7. Proteomic changes associated with high versus usual dose diuretics will be assessed to evaluate for differential expression of key pathways between the two strategies

4.4 .Significance:

1. The demonstration of safety and efficacy with ultra-high dose diuretic strategy compared to conventional diuretic infusion will be an important safety and preliminary efficacy finding to support a multicenter randomized phase III trial for superiority in relation to clinical outcomes.
2. Delineating mechanisms of hemodynamic benefit to more aggressive decongestion and relationship to renal indices will advance our understanding of human cardiorenal syndrome

4.5 Brief Synopsis of Methods:

- Accrual of 20 patients with decompensated heart failure requiring hospitalization randomized to ultra-high vs conventional dose diuretic arms in a double-blind design over 24 hours. Anticipate 25 patients will be enrolled to accrue 20 patients.
- Baseline assessment of renal lohexol clearance, echocardiography, blood sampling and urine sampling and nocturnal Watch Pat one assessment (apnea-hypopnea index), with all above assessments repeated after 24 hours.
- Follow up phone assessment at 90 days to assess heart failure readmission rates.

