5. STUDY DESIGN

This study is a double-blind randomized phase II pilot trial testing the safety and efficacy of ultra-high dose diuretics compared to standard dose diuretics over 24 hours in acute decompensated heart failure. Subjects will be screened after admission to the hospital with decompensated heart failure following stabilization and will be consented and offered participation in the trial. Once consent has been obtained, baseline serum and urine measures will be obtained along with administration of randomized treatment assignment for a total of 2 intravenous doses bid. An ambulatory blood pressure monitor (ABPM) will be worn for a 48 hour period starting from randomization. Additional mechanistic measures including short renal lohexol clearance (2 hour), echocardiography, arterial tonometry, liver elastography, and nocturnal apnea-hypopnea index (Watch Pat) will be performed. Final endpoint assessment with repeat of all baseline measures including lohexol clearance, echocardiography, arterial tonometry, liver elastography, and nocturnal apnea-hypopnea index (Watch Pat) will be performed on Day 2 after the 24-hour intervention. A final phone call visit at 90 days will assess for adverse events and heart failure hospitalization over the post discharge period.

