7.3.4 Adherence Assessment

The number of study drug administered and use of adjunct diuretics outside study protocol will be monitored and collected.

8. **STUDY PROCEDURES**

An overview of the scheduled evaluations is provided in the following table.

Schedule of Events

	Day of Consent (Day 1)	Day 2	Day 7⁴ (-4 days)	Day 90 (Phone visit) (+/- 30 days)
Informed Consent	X			
Physical Exam	X	X		
Randomization to Medical Therapy	X			
Administration of Medical Therapy	X ¹	X ¹		
Iohexol GFR testing	X ²	X ²		
Blood testing (NT proBNP, cystatin C, creatinine, hematocrit,)	X	X	X ⁷	
Research blood	X ³	X ³		
Urine testing (urine sodium, urine creatinine, NGAL, KIM-1)	X ³	X ³		
Electrocardiogram	X ⁵		X ⁶	
Echocardiogram	X	X		
Peripheral vein pressure	X	X		
Nocturnal Watchpat /Nox device screen	X	X		
Arterial Tonometry	X	X		
Ambulatory Blood Pressure	X	X		
Liver Elastography	X	X		
Adverse event assessment		X	X	X
Assessment for re-hospitalization				X
Concurrent medication assessment	X	X		X

¹Administration of Medical Therapy to be a total of 2 intravenous doses bid, administered by inpatient staff nurses

²Iohexol GFR testing (Renal Clearance) to be performed at bedside by CRTU staff

³Blood and urine samples to be collected by CRTU staff. Samples will either be collected by CRTU or transported by study staff to CRTU in tubes on ice when necessary.

⁴Day 7 or day of discharge, whichever is earlier

⁵Baseline ECG clinically indicated. If > 48 hours prior to randomization, must be repeated.

⁶ECG for research for comparison

⁷Estimated GFR at day 7 or discharge (whichever is sooner)

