8.1.2 Enrollment, Baseline, and/or Randomization

After confirming eligibility, informed consent will be obtained. Following consent, patients will be randomized 1:1 to ultrahigh vs standard dose diuretic strategies.

Day 1 (0-24 hours)

After randomization, patients will undergo comprehensive baseline assessment including weight, echocardiogram, history, and physical examination. Initial randomized therapy will be administered at least 6 hours after last clinically administered dose of IV diuretic (or immediately if no IV diuretic has been administered in the last 6 hours). Participants will be urged to void their bladders and discard urine at baseline immediately prior to receiving study drug. All baseline testing will be performed when feasible once consent is obtained. Baseline testing will include blood sample testing for NT proBNP, creatinine, cystatin C and hematocrit. Urine collection for urine creatinine and sodium will be specifically collected timed 1-2 hours after the administration of study diuretic dose to allow estimation of urine sodium excretion. 32 ml of blood and 30 ml of urine will be stored for future analyses. Peripheral venous pressure will be recorded from existing IV lines through pressure transducer monitoring from study team.

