In addition to blood testing as above, Iohexol based GFR calculation using subcutaneously injected-Iohexol and timed samples of blood and urine to calculate GFR will be used for research with a procedure following typical inpatient practice Iohexol based GFR measurement. We will use the short Iohexol protocol with subcutaneous iothalamate injection (Time 0:T0), urine sampling at 1 hour after subcutaneous injection, with total urine volume collected over the 1-hour period (T0 to 1 hour). Urine and serum samples will be collected again approximately 45 minutes later from T60. Serum and urine samples for Iohexol will be collected at two time points after T0: i) T60 and ii) 45 minutes after T60. We will also continuously collect urine from subcutaneous injection until the end of the test, for quality control as per standard clinical practice. If Foley catheter is not present at baseline, participants will be asked to void voluntarily prior to renal study initiation with bladder scanning to confirm residual urine following bladder emptying. Ambulatory blood pressure monitoring (ABPM) will be recorded via an upper arm cuff on the non-dominant arm. Over a 48-hour period (Days 1 & 2), a blood pressure reading will be taken every 30 minutes during the day and every hour at night. Arterial stiffness will be assessed via carotid tonometry and placing a femoral and brachial blood pressure cuff on the upper thigh and upper arm. A liver ultrasound scan (Fibroscan) of the abdominal region will quantify liver elastography and potential liver disease.

Nocturnal screening for apnea-hypopnea index as a measure of sleep apnea will be performed using Watch Pat or Nox device. The Watch Pat is a non-invasive wrist monitor and will be worn overnight to test for sleep apnea. The Nox device is a portable polysomnography device to

measure sleep quality and determine sleep apnea presence. If patients have known sleep apnea, they will continue their home CPAP/BiPAP during the overnight test.

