1.3 Primary and Secondary Outcomes

- 1.3.1 Primary outcome: urine output at 24 hours after initiation of intravenous diuretic.
- 1.3.2 Secondary outcomes: changes in the following measures over 24 hours after initiation of intravenous diuretic:
 - 1.3.2.1 Body weight
 - 1.3.2.2 NT-proBNP change
 - 1.3.2.3 Urine sodium excretion
 - 1.3.2.4 Apnea-hypopnea index
 - 1.3.2.5 Iohexol glomerular filtration rate
 - 1.3.2.6 Peripheral vein pressure
 - 1.3.2.7 Echocardiographic measures of cardiac output, estimated RV systolic pressure, RA pressure, LA strain, LV and RV global longitudinal strain, E/e'

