1.5 Secondary Analysis

- 1.5.1 Linear regression models will be used to estimate the between group difference in 24-hour change in each of the secondary outcomes; 95% confidence intervals will be constructed using t-based methods.

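### Nothing in the plan ensures that the baseline sleep night precedes the first study dose, so the 24-hour change in apnea-hypopnea index will ordinarily subtract a treated night

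*Combined protocol and SAP*

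**What the plan says.** **Outcome and analysis.** SAP 1.3.2 (within section 11.5.1) defines the secondary outcomes as "changes in the following measures over 24 hours after initiation of intravenous diuretic", and item 1.3.2.4 is AHI. SAP 1.5.1 states: "Linear regression models will be used to estimate the between group difference in 24-hour change in each of the secondary outcomes". No baseline covariate is named. Section 3.3(f) also lists AHI change as an exploratory objective.

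**Which recording is the reference.** Section 4.5 includes among the baseline assessments the "nocturnal Watch Pat one assessment (apnea-hypopnea index), with all above assessments repeated after 24 hours". Section 8.1.3 likewise counts the Watch Pat screen among the baseline tests repeated 24 hours later, in the 24-48 hour period.

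**How it is recorded.** Section 8.1.2: "The Watch Pat is a non-invasive wrist monitor and will be worn overnight to test for sleep apnea".

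**When it is recorded.** In the Schedule of Events (section 8), the row "Nocturnal Watchpat /Nox device screen" is marked on the day of consent (Day 1) and on Day 2 only. Consent, randomization and the first administration of study drug are also marked on the day of consent.

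**When dose 1 is given.** Section 8.1.2 sets a minimum gap of 6 hours after the last clinical IV diuretic, with an exception for patients outside that window: "or immediately if no IV diuretic has been administered in the last 6 hours". Section 5 says that after consent "baseline serum and urine measures will be obtained along with administration of randomized treatment assignment", and then lists the sleep recording among additional measures. Section 8.1.2 asks for baseline testing as feasible after consent and sets no general requirement that it be finished before dosing.

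**After dosing.** Section 7.1 gives both doses within 24 hours, after which the treating physicians follow usual care.

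**The concern.** A change score measures a treatment effect only if its reference value predates treatment. Blood tests, an echocardiogram or a two-hour iohexol clearance can be completed before a same-day dose. An overnight recording generally cannot. If the patient sleeps the reference night after dose 1, that night already carries whatever between-arm difference has developed by then, and subtracting it removes that part from the result.

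At stake are the sleep part of objective 3.2(b), objective 3.3(f), and item 6 of section 4.3, which presents the short-term effect on sleep as an open question. A small AHI contrast could be read as no effect on sleep when part of the effect had been subtracted.

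**Working it through.** The plan gives no AHI effect, standard deviation or power, so there is no AHI figure to reproduce. Its only power calculation concerns urine output and does not bear on this point. The check has two parts.

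**1. Timing of dose 1 against night 1**

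From the documents: dose 1 on the day of consent, at once or at least 6 hours after the last clinical IV diuretic; two doses within 24 hours; recordings on Day 1 and Day 2.

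Assumed, because the documents do not say: consent between 08:00 and 18:00; a wait of 0 or 6 hours, with no further clinical IV dose after consent; night from 22:00 to 06:00; doses 12 hours apart.

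With dose 1 at clock hour d, night 1 runs from 22 − d to 30 − d hours after dose 1, and night 2 starts at 46 − d.

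| Consent | Wait (h) | Dose 1 | Night 1, hours from dose 1 | Dose 2 | Night 2 starts, hours from dose 1 |
|---|---|---|---|---|---|
| 08:00 | 0 | 08:00 | 14 to 22 | 20:00 | 38 |
| 08:00 | 6 | 14:00 | 8 to 16 | 02:00 | 32 |
| 12:00 | 0 | 12:00 | 10 to 18 | 24:00 | 34 |
| 12:00 | 6 | 18:00 | 4 to 12 | 06:00 | 28 |
| 16:00 | 0 | 16:00 | 6 to 14 | 04:00 | 30 |
| 16:00 | 6 | 22:00 | 0 to 8 | 10:00 | 24 |
| 18:00 | 0 | 18:00 | 4 to 12 | 06:00 | 28 |
| 18:00 | 6 | 24:00 | −2 to 6 | 12:00 | 22 |

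In none of the eight cases is night 1 wholly before dose 1. In seven it starts at or after dose 1; in the last, dose 1 falls 2 hours into the night. With an 08:00 dose, dose 2 also precedes night 1. Night 2 always starts after dose 2, by 34 − d hours, which is 10 to 26.

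The main step needs no clock times. A night that begins on the consent day ends the next morning, so any dose given on the consent day comes before the end of that recording.

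**2. What the change score then estimates**

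Let D1 and D2 be the true between-arm differences in mean AHI (ultra-high minus standard) on nights 1 and 2. Before dosing, the expected difference is zero by randomization. The planned contrast is

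difference in mean change = D2 − D1.

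It equals D2 only if D1 = 0, as it would be for a wholly pre-dose night. Writing D1 = f × D2 gives D2 × (1 − f). With an assumed D2 of −10 events per hour:

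| f (assumed) | Contrast | Share of D2 |
|---|---|---|
| 0 | −10 | 100% |
| 0.25 | −7.5 | 75% |
| 0.5 | −5 | 50% |
| 0.75 | −2.5 | 25% |
| 1 | 0 | 0% |
| 1.25 | +2.5 | −25% |
| 1.5 | +5 | −50% |

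Adding night-1 AHI as a covariate does not repair this. With regression slope b the adjusted difference is D2 − b × D1, so a post-dose measurement is still being removed.

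**The case against.** **The order is inferred.** No sentence says that night 1 follows dose 1. The 6 hours are a minimum, baseline tests are asked for as feasible, section 8.1.2 labels Day 1 as hours 0-24, and the protocol itself calls the first recording baseline. A site could record a night and dose the next morning. This stands: a pre-dose night is not excluded. But nothing requires one, and the immediate-dosing clause and the dose marked on the day of consent point the other way. A reader might infer that night 1 always falls after dose 1; the documents do not support that as a stated fact.

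**The size is unknown.** Both arms receive an active IV loop diuretic, so D1 is only the difference between arms on night 1, and an effect common to both cancels. If D1 is smaller than D2 and has the same sign, the contrast keeps its sign and is merely attenuated. This also stands. A reader might infer that the change score will hide or reverse a real effect. That needs a night-1 difference at least as large as that on night 2, a time course the documents neither support nor exclude.

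**Within-patient adjustment is valuable.** Groups are small, about 10 per arm, and patients with known sleep apnea keep their home CPAP or BiPAP during the test, so AHI levels may differ widely between patients. That is a genuine cost, but it does not make a treated night a valid reference.

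**The weight is modest.** AHI is one of many secondary measures in a 20-patient pilot with unadjusted p-values. Both nights are recorded, so nothing is irretrievably lost. This limits the importance of the point but does not remove it.

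**Conclusion.** The concern holds in a limited form. The plan does not ensure a pre-dose reference for AHI, and its schedule and dosing rule make a wholly pre-dose night unlikely. Followed as written, the analysis will ordinarily subtract a treated night and so estimate D2 − D1.

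The expected consequence is attenuation by the fraction of the between-arm effect already present on night 1. That fraction cannot be computed from the documents; across assumed values from 0.25 to 0.75, the contrast recovers 75% to 25% of the night-2 effect. A null or reversed contrast is possible but hypothetical.

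Nor should a reader conclude that the sleep question cannot be answered from this trial. Randomization protects a direct comparison of AHI between arms on either night, using recordings already planned. The flaw is confined to the change score and the baseline label. The primary urine-output endpoint is untouched.

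**What to change.** - **SAP 1.3.2.4 and 1.5.1.** Replace the AHI change score with two between-arm comparisons of AHI level: night 1 (on treatment) and night 2 (24-48 hours). Name one of them in advance as the main AHI outcome.
- **Data capture.** Record the start and end of each recording relative to dose 1.
- **Change score.** Report it only as a descriptive supplement. Do not use night 1 as a baseline for the subset who happen to be recorded before dosing in the main AHI analysis; that would mix two different quantities in about 20 patients.
- **Wording.** Align the AHI text in the Study Summary (study product row) and in sections 4.5, 5, 8.1.3 and 11.4.2.1, so that the Day 1 night is not described as a pre-treatment baseline and AHI is not described as a 24-hour change.

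**Cost.** Wording changes and the recording times; no new procedure, and no change to dose timing is proposed. The statistical price is precision. With equal variance σ² on both nights and between-night correlation ρ, a change has variance 2σ²(1 − ρ) against σ² for a level, so the level comparison gives wider intervals when ρ exceeds 0.5. That is plausible here, but the documents give no value for ρ.

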8.1.3 Follow-up Visits

Day 2 (24-48 hours)

All baseline testing including blood sampling and storage, urine sampling and storage, short Iohexol clearance, history/physical including weight, echocardiogram, arterial stiffness, liver scan, and nocturnal Watch Pat screen will be repeated 24 hours after initial assessment. ABPM will continue and terminate after 48 hours of blood pressure recording. Following this all study-related procedures will be complete. Hospital length of stay and total diuretic use will be documented. Clinical creatinine measurements obtained at Day 7 or discharge will be recorded for exploratory analyses. All AE's will only be collected for Days 1 through Day 7.

Day 90

Phone call to review hospitalizations, AEs, and concomitant medications. Re- Hospitalizations will be collected as AEs, not lab values. Following this all study-related procedures will be complete.

9. SAFETY ASSESSMENTS

9.1 Adverse Drug Reactions and safety aspects with bumetanide

Muscle aches and myalgias is a known side effect of bumetanide and will be assessed by a Likert questionnaire (scale 0-10). New onset atrial fibrillation, ventricular tachycardia will be assessed by review of telemetry monitoring. Blood pressure will be assessed before administration of each diuretic dose and if blood pressure is <80 mm Hg this will be reviewed by the PI and clinical team before administering subsequent diuretic dose.

9.2 Adverse Drug Reactions and safety aspects with furosemide

Adverse reactions will be recorded as above for bumetanide.

9.3 Specification of Safety Parameters

Renal function panel will be checked at least twice as is standard practice during intravenous diuresis and K and Mg replacement will be adjusted as per electrolyte panel checks with oral KCl and Mg repletion utilized as per clinical practice. Intravenous repletion will be used when oral therapy is not tolerated. In the presence of substantial hypokalemia (K<2.9 mEq/dl), the subsequent diuretic dose will be held until K repletion has been administered.

Blood pressure monitoring prior to each dose will ensure hemodynamic stability prior to administration of subsequent diuretic dose. If the systolic BP is <80 mmHg this will be reviewed by the PI and clinical team before administering subsequent diuretic dose.

During arterial stiffness measures, if aortic pulse pressure is greater than 50 mmHg (derived from brachial BP), we will forgo carotid tonometry and femoral blood pressure measures.

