7.3.3 Prohibited Interventions

Patients should not be on drugs that can significantly increase the risk side effects with bumetanide and furosemide, i.e., inotropic medications. New initiation of additional diuretic agents for synergistic diuresis (thiazide, acetazolamide, SGLT2 inhibitors and spironolactone) will be discouraged during the 24 hour study period to avoid electrolyte imbalance with potential randomization to very high dose diuretic arm. Following the 24 hour study period, addition of other diuretics and medications is as per the treating team per standard of care.

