12.2 Data Management

All study data will be collected at Mayo Clinic with the Department of Cardiovascular Diseases as the primary coordinating and data management center.

REDCap will be used for clinical data management and randomization. These tools are institutionally supported and allow for rapid database development. The implementation of the software within a project includes training on the system's use, robust error checking, security considerations, and full audit trail. Balance, which is integrated into *REDCap*, allows for a variety of randomization and minimization algorithms.

Demographic and clinical data will be extracted from medical records including age and gender, vital signs, physical exam findings.

For biospecimens, NT-pro-BNP, creatinine, hematocrit and cystatin C, urine sodium will be measured in real time, and the remainder will be stored for future analysis of cardiac biomarkers.

The echocardiographic parameters that will be captured comprise: systolic, diastolic LV and RV function parameters including LVEF by M-Mode, 2 D, biplane Simpson, lateral and medial E/e', left atrial volume index, right ventricular size and function, tissue velocities of the tricuspid annulus, TAPSE, lung ultrasound for B lines, IVC diameter/collapse, internal jugular dimension/size relative to carotid.

All individually identifiable patient records and data will be stored in a database under coded accession numbers. A password is required to gain access to this protected and privileged information. Only the approved and trained study staff will have access to the database. For individuals providing data, e.g., core laboratory personnel, access will be limited to entering data only. All data are monitored regularly for entry and access, and a formal policy regarding protection of personal privacy is in place throughout Mayo Foundation. The key to identification of subjects will be maintained in a secure office environment under the direction of the investigators. The institutional commitment at Mayo Clinic to protect patients' (and study participants') privacy is a high priority.

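### Section 9.3 prints the potassium hold threshold in the wrong unit (mEq/dl instead of mEq/L), and no supplied section asks for a potassium review before dose 1

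*Combined protocol and SAP*

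**What the plan says.** Section 9.3 (Specification of Safety Parameters) carries the only potassium rule in the supplied text: "In the presence of substantial hypokalemia (K<2.9 mEq/dl), the subsequent diuretic dose will be held until K repletion has been administered". On monitoring, the same section says: "Renal function panel will be checked at least twice as is standard practice during intravenous diuresis". It adds that potassium and magnesium replacement follows the electrolyte results. It does not say when either panel is drawn relative to a study dose.

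Section 7.1 gives two study doses within 24 hours. For dose 1, Section 8.1.2 sets a waiting rule: "Initial randomized therapy will be administered at least 6 hours after last clinically administered dose of IV diuretic". If no IV diuretic was given in the last 6 hours, dosing may be immediate. The same section lists the study baseline bloods: "Baseline testing will include blood sample testing for NT proBNP, creatinine, cystatin C and hematocrit". It also says: "All baseline testing will be performed when feasible once consent is obtained". No exclusion criterion in Section 6.2 concerns potassium.

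Blood pressure is handled differently. Sections 9.1, 9.3 and 9.4 each place its check before every study dose.

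Section 7.3.3 shows that the sponsor has electrolytes in mind. New adjunct diuretics are discouraged "to avoid electrolyte imbalance with potential randomization to very high dose diuretic arm".

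**The concern.** The first issue is the printed threshold. A hold rule is a decision rule that staff apply at the bedside, so its number and unit have to be right. This one is out by a factor of ten.

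The second issue is when the rule can act. A hold works only if someone has a result in hand before the dose. Entrants are already on IV diuretics (Section 6.1), so a low potassium before dose 1 is plausible. In the high-dose arm, dose 1 is 12.5 mg of bumetanide. As written, a patient below the sponsor's own threshold could receive dose 1 with no deviation from the protocol if nobody had looked at a recent value. What is at stake is patient safety at the start of treatment. The primary analysis is not affected.

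**Working it through.** **Unit.** Input: the threshold printed in Section 9.3, 2.9 mEq/dl. There are 10 dl in a litre.

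- Literal threshold: 2.9 mEq/dl × 10 dl/L = 29 mEq/L.
- Ratio to the intended threshold: 29 / 2.9 = 10.

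No patient has a serum potassium as high as 29 mEq/L, so the literal condition is true for everyone. The next dose would always be held, and everyone would be given potassium before it was released. No one would act on that, and the sentence itself speaks of substantial hypokalemia. The documents never print mEq/L. The corrected unit is therefore inferred from physiology, but no other reading is workable.

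**Timing.** The relevant sections, side by side:

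| Check | Before dose 1 | Before dose 2 |
|---|---|---|
| Blood pressure (9.1, 9.3, 9.4) | stated | stated |
| Potassium (9.3) | not stated | implied by the hold rule, draw time not stated |

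- Dose 2: only two doses are given. A rule that holds the next dose on a low value, together with two or more panels during diuresis, makes sense only if a result is seen between the doses. The check is implied, although no draw time is written.
- Dose 1: the word for the next dose in 9.3 might be stretched to cover dose 1, since a check could come before it. Even so, nothing requires a result to be available then. The one stated timing condition for dose 1 is the 6-hour gap in 8.1.2, which falls away when no recent IV diuretic was given.

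**Context for dose 1 in the high-dose arm.** Section 10 cites 10 mg as the commonly recommended daily maximum of bumetanide, and says that figure does not rest on data.

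- Dose 1 alone: 12.5 / 10 = 1.25 times that maximum.
- Both doses: 2 × 12.5 = 25 mg, and 25 / 10 = 2.5 times.

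These ratios explain why a look at potassium before dose 1 is sensible. They do not measure the gap, and they apply to one arm only. Section 10 also reports use of the same bolus in current practice with no apparent serious adverse events.

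**Panels.** Section 9.3 requires at least 2. If both were used as the two pre-dose results, 2 − 2 = 0 required results would remain after dose 2, when cumulative exposure is highest. If dose 1 relies on an existing clinical result instead, one required panel can fall between the doses and the other after dose 2. The added number of required panels is then 2 − 2 = 0, except in a patient with no recent clinical value, who needs one more.

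**The case against.** The strongest reply is that potassium is already well covered. Patients are on IV diuretics and enrolled after stabilization. Section 9.3 describes panel-guided replacement as usual care, 7.3.1 allows all necessary treatment, and telemetry is reviewed (9.1). Applying the exclusion for stage V kidney disease and fixing a baseline creatinine also require recent renal results. Most of this stands: a low value that nobody has seen before dose 1 should be uncommon. None of it says that the value is reviewed before dosing.

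A reader might go further and infer that potassium is unchecked for both doses. The text does not support that, because the rule in 9.3 implies a check before dose 2.

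A reader might also take the study test lists as proof of a gap. The Schedule of Events has "Blood testing (NT proBNP, cystatin C, creatinine, hematocrit" and Section 12.2 has "NT-pro-BNP, creatinine, hematocrit and cystatin C, urine sodium will be measured in real time"; like the list in 8.1.2, neither includes serum potassium. These lists cover study measurements, however. Clinical safety panels are specified separately in 9.3, so the omission shows nothing by itself. The phrase about feasibility in 8.1.2 likewise concerns study baseline testing.

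Finally, the contents list a Data and Safety Monitoring Plan as an appendix, and it is not in the supplied text. The timing point is limited to what was supplied. If that plan already times potassium, 9.3 need only refer to it.

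**Conclusion.** The unit in 9.3 is wrong as written, by a factor of ten. The intent is clear and the literal error fails safe on dosing, so this is a correction of a safety threshold and not evidence of likely harm.

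The timing point is secondary and narrower. In the supplied text no sentence requires a potassium result to be reviewed before dose 1, while a check before dose 2 is implied. The number of patients who would reach dose 1 with a missed low potassium is probably small. It cannot be estimated, because the documents give no potassium frequencies. The conclusion assumes that the renal panel in 9.3 includes potassium, as the replacement sentence there suggests, and that the absent appendix does not already settle the timing.

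**What to change.** In Section 9.3, change mEq/dl to mEq/L. Then add, for both arms, text along these lines: the most recent clinical potassium is reviewed before each study dose. For dose 1 this is an existing clinical result, for example from the previous 24 hours. For dose 2 it is one of the panels already required, drawn between the doses. If the value is below 2.9 mEq/L, that dose is held until potassium repletion has been given. The other required panel is kept for after dose 2. The 24-hour window is a proposal and has no source in the documents, so the sponsor may prefer another.

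The cost is one unit correction and a few sentences, with no new exclusion criterion and no research blood draw. The downside is an occasional short dose delay:

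- **Dose 1.** When the 6-hour wait in 8.1.2 applies, it will usually leave time for a result. A patient who could otherwise be dosed at once, and has no recent potassium, would wait for one. The primary endpoint window is not shortened, because Section 11.5.1 (1.3.1) counts 24 hours from the start of the IV diuretic. Section 8.1.3, however, repeats the assessments 24 hours after the initial ones. If baseline testing is done and dose 1 is then delayed by d hours, Day 2 weight, NT-proBNP and iohexol GFR would reflect only 24 − d hours of treatment. Those assessments should therefore be timed from the first study dose.
- **Dose 2.** A delay here falls inside the primary window, but the existing hold rule already allows it.
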